GA	=	general anesthesia
POD	=	postoperative day
PACU	=	post anesthesia care unit
EPIC	=	electronic privacy information center
REDCap	=	Research Electronic Data Capture (Cleveland clinic internal database)
PCA	=	Patient controlled Analgesia
NRS	=	Numerical rating scale
GEn	=	Gabapentin enacarbil

CONTENTS

[figure not shown]
Word did not find any entries for your table of contents.

[figure not shown]
In your document, select the words to include in the table of contents, and then on the Home tab, under Styles, click a heading style. Repeat for each heading that you want to include, and then insert the table of contents in your document. To manually create a table of contents, on the Document Elements tab, under Table of Contents, point to a style and then click the down arrow button. Click one of the styles under Manual Table of Contents, and then type the entries manually.

RESEARCH SCHEMA

Title	A randomized controlled trial to determine the effect of gabapentin enacarbil on opioid consumption and pain scores in patients having hip and knee arthroplasties with spinal anesthesia
Short Title	PAIN ATTENUATION IN SURGICAL PATIENTS
Principal Investigator	[name]
Primary Objectives	To assess whether gabapentin enacarbil decreases pain and/or opioid requirements after hip or knee surgery
Secondary Objectives	- To assess whether gabapentin enacarbil decreases the incidence of persistent incisional pain three months after surgery when used as a modality of pre-emptive analgesia. - To evaluate whether gabapentin enacarbil decreases nausea and vomiting during the initial 72 post-operative hours. - To evaluate whether gabapentin enacarbil reduces the duration of hospitalization. - To evaluate whether gabapentin enacarbil improves patient's satisfaction
Study Design	A randomized, double-blind, placebo-controlled, single institution trial
Inclusion Criteria	1. Men or women 18-85 years of age. 2. Scheduled for elective total primary knee or total primary hip arthroplasty with spinal anesthesia.
Exclusion Criteria	1. Creatinine >1.50 mg/dl. 2. History of clinically important current depression or currently on any prescribed anti-depressant medication. 3. Previously enrolled in any Xenoport trial. 4. Use of gabapentin or gabapentinoids (Lyrica, Horizant, Neurontin or Gralise) with one month. 5. Allergy to gabapentin or gabapentinoids (Lyrica, Horizant, Neurontin or Gralise). 6. Women who are pregnant or breastfeeding. 7. History of seizure disorder within the last one-year or taking medications for seizure
Expected Sample Size	100 Patients
Statistical Methodology	We will consider gabapentin enacarbil group better than placebo group on the postoperative pain management if gabapentin enacarbil group is found noninferior (i.e., not worse) on both outcomes and superior on at least one of the outcomes. We define the a-priori noninferiority pain score delta as 1 point and the opioid delta as

	1.1 for the ratio in geometric means IV morphine equivalent doses (meaning 10% difference between group's median doses).
--	---

1. INTRODUCTION

1.1 Background

Pain control

Hip and knee replacements are the most common elective surgeries in the U.S.A. Pain control after surgery remains challenging despite advances in surgical techniques and new treatment modalities (32-33). Three-quarters of surgical patients in the United States experience postoperative pain and are unsatisfied with their analgesia (28-29). The major cause of pre-operative anxiety in any surgical patient is fear of postoperative pain (18). Pain is a psychological sensory experience, which is caused by various factors. Surgery results in tissue damage which leads to postoperative pain. Studies in recently developed animal models of postoperative pain have advanced our knowledge of the mechanisms of pain resulting from surgical incision and associated tissue injury.

Post-operative pain has numerous etiologies and many contributing factors; it thus usually responds best to multimodal approaches (28-29). Pain may result from tissue trauma secondary to stretching and compression or direct nerve injury as a result of surgical incisions and burns (1-6). Pain is aggravated by coughing, sneezing, moving etc. or any other movement, which increases pressure over the surgical area. Most clinicians consider nerve blocks to be the optimal approach, but many patients nonetheless require opioids.

Ineffective pain control results in increased mortality and morbidity (7-8, 22). For example, surgery provokes immune depression, which may have deleterious effects. Reducing postoperative pain may speed mobilization and reduce pulmonary and cardiac complications, whereas early mobilization reduces the risk of deep vein thrombosis. This implies that, if post-operative pain is treated effectively, then costs of care could be decreased significantly.

1.2 Gabapentin enacarbil

Gabapentin is an analog of gamma-aminobutyric acid. It is currently approved by the US Food and Drug Administration for treatment for post herpetic neuralgia and seizure disorders. It binds to alpha-2 delta subunit of presynaptic P/Q voltage gated calcium channels, which regulate the release of excitatory neurotransmitters from nociceptive receptors (4). Gabapentinoids can decrease post-operative pain by regulating glutamate release through the calcium channels and also through activation of inhibitory noradrenergic pain pathways in the spinal cord and brain. Gabapentin is absorbed through the duodenum, only minimally protein bound and renally excreted. Antacids interact with gabapentin to impair its absorption.

Gabapentin reaches peak plasma concentrations about two hours after oral administration, and its half-life is between 4.8-8.7 hours; hence, it is given in two daily doses. Since gabapentin is renally excreted, the dose should be reduced in patients with renal dysfunction, especially when creatinine > 1.50 mg/dl (15-16). Side effects include sedation, dizziness, headache, visual disturbances, and peripheral edema (17).

Peri-operative use of gabapentin reduces early post-operative pain and opioid consumption (9-11). Postoperative delirium a complication of general anesthesia is less common after gabapentin administration (24). In 2012, Mahdi Panah Khahi et al compared visual analog scores and fentanyl use in patients given gabapentin pre-operatively and immediately post-incision via nasogastric tube. Patients given gabapentin preoperatively had lower visual analog scores and required less fentanyl than those given the drug later (30).

In another study, less morphine was required in patients given gabapentin both pre- and post-operatively than just pre-operatively. A knee-flexion test was used to check the efficacy of post-operative gabapentin on post-operative pain, which revealed better flexion in patients using both pre- and post-operative gabapentin (12). In a qualitative and quantitative review in patients who had abdominal hysterectomy and spinal surgery, gabapentin decreased pain scores, use of narcotics and symptoms like nausea and vomiting when given pre and peri-operatively(31,34).

A study by Panah Khahi et al revealed that pre-emptive use of gabapentin reduced pain scores on both post-operative day 1 and day 2 and use of opioids in orthopedic patients undergoing internal fixation of tibia (13). Using high dose gabapentin (600 mg) lead to lower pain scores than low dose 300 mg in patients who had lumbar discectomies. Similarly, preemptive use of 600 mg gabapentin orally in patients undergoing abdominal hysterectomies required low amounts of analgesic and antiemetics (14, 20, and 23).

1.3 Clinical Data to Date

Multimodal approach

Opioids are effective analgesics, but cause side effects including sedation, respiratory depression, hypotension, nausea, and constipation. Hence, opioids are often combined with local anesthetics, non-steroidal anti-inflammatory drugs (NSAIDs), acetaminophen, ketamine, or other agents in an effort to reduce postoperative pain while minimizing side effects, an approach termed “multimodal analgesia” (25-27). NSAIDs are antipyretic and anti-inflammatory, but provoke surgical and gastrointestinal bleeding; renal impairment and they also impair bone healing. The main goal is to decrease opioid use and consequently decrease the incidence of opioid related side effects. Non-opioid analgesics used in this are generally insufficient to treat postoperative pain by themselves, but have substantial opioid sparing effects and thus presumably reduce opioid-related complications.

In summary, opioids provoke numerous severe complications that cause substantial patient morbidity. They also delay discharge from hospital, increase the cost of care, and reduce patient satisfaction.

Multimodal analgesia is believed to decrease length of hospitalization, decrease the cost of care, and shorten recovery (19-21). Multimodal analgesia a decrease opioid use, and hence is thought to indirectly reduce opioid-induced side effects and complications including respiratory depression and ileus. NSAIDs, acetaminophen, ketamine, and pregabalin have been tried in the past as adjuncts to decrease overall consumption of opioids. Acetaminophen is opioid sparing, but must be used cautiously in patients with impaired liver function (35, 36, and 37).

The impact of postoperative opioid related complications is not only important from a clinical perspective, but also from an economic standpoint. The additional cost attributable to opioid side

effects has not been well defined and usually depends on estimates rather than solid data. Our study will provide data to support a full cost-benefit analysis, so the financial benefits of GEN can be concretely evaluated. We thus propose to evaluate the opioid-sparing effect of GEN and, more importantly, the reduction in opioid-related complications.

1.4 Dose Rationale and Risk/Benefits

We would like to test an extended-release formulation of gabapentin enacarbil, a prodrug of gabapentin, a FDA approved drug for post herpetic neuralgia and restless leg syndrome (43). Extended release gabapentin enacarbil and gabapentin are different in their pharmacokinetics and have variable but predictable bioavailability (39). This results in different plasma concentrations at the same doses (39). It is shown to provide dose-proportionality and extended exposure to gabapentin over the range 300 to 6,000 mg (39). At high doses gabapentin transporters in the intestines get saturated, this could be overcome by using an extended release formulation with predictable dose proportional bioavailability (38). GEN is absorbed via high capacity nutrient transporters located throughout the intestinal tract thus providing a predictable dose proportionality and improved bioavailability. A 600 mg dose of gabapentin enacarbil produces at least 312 mg of gabapentin on hydrolysis (39, 40).

A more predictable gabapentin exposure is achieved due to linear relationship of dose-exposure for gabapentin enacarbil and hence the dosing frequency could be decreased (41). Per PI Tmax of gabapentin after 600 mg (Horizant) is 5.0 hours (fasted) and 7.3 hours (fed). GEN provides more sustained dose proportional exposure to gabapentin (unlike gabapentin), which may lead to more predictable exposure with GEN and decreased dosing frequency relative to gabapentin. Due to the mechanism of action of GEN and its predictable bioavailability due to its absorption via the MCT-11 transporters, we would like to prefer GEN to gabapentin.

We thus propose to test the hypothesis that gabapentin enacarbil when used as a modality of pre-emptive analgesia decreases opioid consumption and/or decreases pain scores in hip and knee arthroplasty surgery.

2. STUDY OBJECTIVES

Primary and secondary objectives

The primary objective of this study is to compare the efficacy of gabapentin enacarbil 600 mg BID taken 1 day pre-op and approximately 2 hours before the surgery and restarted within 6 hours of completion of surgery and then 3 days post-operative versus placebo in reducing the use of opiates and/or pain scores in post-hip and knee arthroplasty surgery patients with spinal anesthesia.

Using a randomized design and blinded assessments, our goal is to determine whether Gabapentin enacarbil when used as a modality of pre-emptive analgesia decreased opioid consumption and/or decreased pain scores in hip and knee arthroplasty surgery.

The proposed research will have the following aims:

Primary objectives include:

Primary Aim 1: To assess whether gabapentin enacarbil decreases pain and/or opioid requirements after hip or knee surgery.

Hypothesis: Patients received gabapentin enacarbil will have less pain scores and/or less opioid consumption during the initial 72 hours after hip or knee surgery compared to patients who received placebo, and not worse on either outcome.

Secondary objectives include:

Secondary Aim 1: To assess whether gabapentin enacarbil decreases the incidence of persistent incisional pain three months after surgery when used as a modality of pre-emptive analgesia.

Hypothesis: Gabapentin enacarbil decreases the persistence of incisional pain three months after surgery.

Secondary Aim 2: To evaluate whether gabapentin enacarbil decreases nausea and vomiting during the initial 72 post-operative hours.

Hypothesis: The incidence of postoperative nausea and vomiting is reduced in patients given gabapentin enacarbil during the initial 72 hours after hip and knee replacement surgery.

Secondary Aim 3: To evaluate whether gabapentin enacarbil reduces the duration of hospitalization.

Hypothesis: The duration of hospitalization after knee or hip arthroplasties is reduced in patients given gabapentin enacarbil.

Secondary Aim 4: To evaluate whether gabapentin enacarbil will improve patient's satisfaction.

Hypothesis: Patients are more satisfied with the pain and quality of life after taking gabapentin enacarbil compared to placebo, as assessed using the quality of recovery score (QoR-15).

3. STUDY DESIGN

3.1 General Design

A randomized controlled trial to determine the effect of gabapentin enacarbil on opioid consumption and pain scores in patients having primary hip or knee replacement surgery with spinal anesthesia. Randomization will be web-based and stratified by type of surgery. Allocation will be concealed until shortly before drug/placebo administration.

Participating patients will be randomly assigned to standard management with GEN or to standard management with placebo. Patients will be given GEN 600 mg bid or placebo 600 mg bid for 1 preoperative day and will receive 600 mg GEN or placebo about 2 hours before surgery and then restarted on GEN or placebo 600 mg within 6 hours of surgery, and then 600 mg bid for three additional days.

3.2 Primary Study Endpoints

To assess whether gabapentin enacarbil improves quality of postoperative analgesia characterized by decreased pain and/or opioid requirements after hip or knee surgery. Cumulative opioid consumption in the PACU and floor for the first 72 hours after surgery or till discharge whichever comes first. The total dose of opioid administered includes the background analgesia provided by morphine PCA, fentanyl PCA or hydromorphone PCA, rescue doses of IV fentanyl, IV

hydromorphone, and PO oxycodone. All opioids will be converted into morphine equivalents to standardize opioid consumption (10 mg of IV morphine = 100 mcg of IV fentanyl = 1.5 mg of IV hydromorphone = 20 mg of PO oxycodone) the total number of requested PCA boluses will also be recorded, along with the number of requests that were actually delivered.

Postoperative pain intensity will be evaluated in the PACU using a 0-10 Numeric Rating Scale (NRS), where 0 is no pain and 10 is the worst possible pain. Pain will be assessed every 15 min for the first one hour after surgery and then every morning for three post-operative days as long as the patients are hospitalized.

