4.5 Data Collection and Follow Up for Withdrawn Subjects

1. Data obtained from electronic medical records will include: operation time, surgery type, intraoperative opioid consumption, postoperative opioid consumption in PACU and in ward, breakthrough pain medication requirements, pain scores in PACU and ward, requirement of antiemetics for nausea and vomiting, requirement of antihistaminic medications, requirement of laxatives for constipation, ambulation time, flatus, ileus, bowel movements, length of stay and any side effects or complications.
2. Preoperative and postoperative laboratory data including but not limited to renal function results will also be collected from electronic medical records. Patient functionality will also be recorded including, bathing, toileting, walking and moving.
3. Patients will be evaluated for pain (using numerical rating scale) (NRS) once in the PACU (Post-Anesthesia Care unit) every 15 minutes during the initial first hour after surgery and then on the first, second and third post-operative morning. Amount of opioids used, rescue anti-emetics used, nausea, vomiting and pain scores will be documented in EPIC.
4. With all study patients, post-operative pain at rest will be collected and reflected using the Numerical rating scale (NRS) pain scale. The patient is asked to rate the pain within (0-10), with zero indicating no pain and 10 indicating the worst imaginable pain.
5. Pain will be evaluated both at rest and after exercise as per physiotherapy protocol. This would be a global assessment of pain since the last assessment.
6. Patient satisfaction with their pain treatment will be questioned after 72 hours or at discharge whichever comes first using 0-5 scales and we will also use QoR-15 score to formally evaluate quality of recovery. The QoR-15 score is a validated scoring system allows quantification of patient's early postoperative health status, which is also a

description of quality of recovery. The QoR-15 score will be performed on 72 hours post op or at discharge whichever comes first.

7. Patients will be contacted by telephone at 3 months after surgery and queried regarding presence of new pain since surgery and its interference with activities of daily living. Phone call is made with the purpose of checking for pain conversion from acute to chronic and to check for any adverse event.

5. STUDY DRUG (or Device, Biologic, Treatment)

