6.2 Visit 1 (Day of Surgery)

Patients will be given GEn 600 mg single dose with sips of water 2 hours before surgery and then restarted within 6 hours of completion of surgery. GEn will be administered to the patient 600 mg bid for three post-operative days with meals.

Physical evaluations include monitoring vital signs, checking general well-being and pain evaluation both pre-operatively and post-operatively. Patients will be evaluated by orthopedic

surgeons pre-operatively and post-operatively as per their protocol. Physical therapy will evaluate the patients for pain, mobility and strength as per physical therapy protocol. Physical therapy and orthopedic surgeons will record and document their findings in EPIC.

Patients will be monitored throughout their stay in the hospital and will be asked to report any adverse event or any untoward event to the research fellow. Patients will be also be inquired for any side effects during the phone call made 3 months after surgery.

Patient discharged prior to 72 hours will be followed-up via phone call(s). Phone call followup will be performed once a day till 72 hours.

6.3 Visit 2 (Phone call).

Patients will be contacted by telephone at 3 months after surgery and queried regarding presence of new pain since surgery and its interference with activities of daily living. Phone call is made with the purpose of checking for pain conversion from acute to chronic and to check for any adverse event.

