⁵ Physical evaluations include monitoring vital signs, checking general wellbeing and pain evaluation both pre-operatively and post-operatively. Patients will be evaluated by orthopedic surgeons pre-operatively and post-operatively as per their protocol. Physical therapy will evaluate the patients for pain, mobility and strength as per physical therapy protocol. Physical therapy and orthopedic surgeons will record and document their findings in EPIC.

⁶ Patients will be monitored throughout their stay in the hospital and will be asked to report any adverse event or any untoward event to the research fellow. Patients will be also be inquired for any side effects during the phone call made 3 months after surgery.

⁷ Data will be collected through personal interview and through electronic medical records. Data will also be collected through the phone call made 3 months after surgery.

Pre-operative data collection:

1. Pain scores using numerical rating scores (NRS) during the pre-operative evaluation visit
2. Brief pain inventory (BPI) at pre-operative evaluation visit.
3. Demographic data to be obtained includes height (cm), weight (kg), age (yr.), gender, (ASA) physical status, and self-declared ethnicity.
4. Patients will be questioned for social history (tobacco) and medical history (pulmonary disease, kidney disease, diabetes mellitus, neurological disease, chronic pain conditions, illegal drug usage, alcohol abuse, myocardial infarction, previous surgery or stent placement and medications usage).
5. Available preoperative laboratory tests and medication list will be recorded.
6. Individual risk for nausea and vomiting will be determined using the Apfel score.

Post-operative data collection:

1. Pain scores using numerical rating scores (NRS):
 - a. Every 15 minutes for the first hour after surgery.
 - b. Every four hours after the first hour until 72 hours after the surgery.
2. Brief pain inventory (BPI) prior to hospital discharge or at 72 hours post op whichever comes first
3. The QoR-15 score to formally evaluate quality of recovery. The QoR-15 score is a validated scoring system allows quantification of patient's early postoperative health status, which is also a description of quality of recovery. The QoR-15 scoring will be done prior to hospital discharge or at 72 hours post op whichever comes first.

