7.2 Statistical Methods

The modified intention-to-treat approach will be utilized: patients who were randomized, had the procedure and received any amount of treatment will be included in the analysis. The per-protocol analysis (on patients who were randomized, had the procedure and followed the treatment regimen at least 50% of the times) will be conducted for the primary outcome as a sensitivity analysis.

First, randomized groups will be compared for balance on potentially confounding baseline demographic and preoperative variables using descriptive statistics.

Primary outcome. In the primary hypothesis, quality of postoperative analgesia will be characterized using both pain scores and total postoperative opioid consumption within 72 hours of the surgery or till discharge. We will consider gabapentin enacarbil group better than placebo group on the postoperative pain management if gabapentin enacarbil group is found noninferior (i.e., not worse) on both outcomes and superior on at least one of the outcomes. We define the a-priori noninferiority pain score delta as 1 point and the opioid delta as 1.1 for the ratio in geometric

means IV morphine equivalent doses (meaning 10% difference between group's median doses). Thus, our primary hypothesis will be assessed in a joint hypothesis-testing framework described by Mascha and Turan (42).

We will first estimate confidence intervals for the treatment effect for both pain score and opioid consumption. Assuming lognormal distribution of opioid consumption, we will evaluate the percent difference in geometric mean IV morphine equivalent dose between the two groups using a log-linear regression model. To evaluate the difference in mean pain scores we will first summarize the pain scores by computing time weighted average (TWA) pain score for each patient. Then we will use a linear regression model to assess the treatment effect on the TWA pain scores.

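### The primary opioid total stops at discharge, which the drug is hypothesised to bring forward, and the pain observation window is stated inconsistently

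*Combined protocol and SAP*

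**What the plan says.** - **Hypothesis.** Primary Aim 1 (Section 2) compares pain and opioid use "during the initial 72 hours after hip or knee surgery compared to patients who received placebo". It mentions no discharge cut-off.
- **Opioid endpoint.** Section 3.2 counts "Cumulative opioid consumption in the PACU and floor for the first 72 hours after surgery or till discharge whichever comes first". Section 7.2 repeats the limit: "total postoperative opioid consumption within 72 hours of the surgery or till discharge".
- **Expected effect on stay.** Secondary Aim 3 (Section 2) states: "The duration of hospitalization after knee or hip arthroplasties is reduced in patients given gabapentin enacarbil".
- **Analysis.** Section 7.2 fits a log-linear regression to each patient's total morphine-equivalent dose. It states no offset, rate or term for time observed. The only sensitivity analysis is per-protocol.
- **After early discharge.** Section 6.2 says "Phone call followup will be performed once a day till 72 hours", and the Section 6.4 calendar marks these calls on postoperative days 2 and 3. Nothing says that they collect opioid doses or pain scores.
- **Pain schedule.** After the first hour, Section 3.2 has scores "every morning for three post-operative days as long as the patients are hospitalized". Section 4.5, item 3, has them "then on the first, second and third post-operative morning". Section 6.4, footnote 7, has them "Every four hours after the first hour until 72 hours after the surgery".

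**The concern.** Discharge happens after randomisation, and the trial itself hypothesises that treatment affects it. A cumulative dose that stops at discharge therefore mixes two things: how much opioid patients use, and how long someone counts it. A shorter stay on the drug lowers its total with no change in hourly use. A longer stay raises the total and can hide a real saving. Opioid consumption is the outcome on which the trial is powered, and it also carries a noninferiority test.

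The time-weighted average (TWA) pain score does divide by time. Averages over different windows still cover different stretches of recovery, so the two arms may not be compared like with like. The direction of that bias depends on how pain evolves.

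**Working it through.** **Inputs from the documents.** 50 patients per arm, coefficient of variation 0.7, target ratio 0.63 and level 0.0125 (Section 7.1). One-tailed superiority tests at 0.0125, noninferiority at 0.025, margins of 1.1 (opioid ratio) and 1 point (pain) (Section 7.2).

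**Assumptions.** Mean observation windows by arm, the opioid time course, the pain trajectory, a pain SD of 1.5 or 2, and independence of the two outcomes. The documents give none of these.

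**1. The plan's own power.**
- Log-scale SD = √ln(1 + 0.7²) = 0.6315.
- SE of the log ratio = 0.6315 × √(2/50) = 0.1263.
- Noncentrality = |ln 0.63| / 0.1263 = 0.462 / 0.1263 = 3.66.
- A one-sided t-test with 98 df at 0.0125 gives 91.5% power. The plan's figure of about 90% reproduces.

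**2. Ratio produced by the window alone, with equal hourly use in both arms.**
- Constant use: T(drug) / T(placebo).
- Declining use: (1 − e^(−kT(drug))) / (1 − e^(−kT(placebo))), with k = ln 2/24 or ln 2/12 per hour.
- Example, 48 h against 60 h with use halving every 24 h: (1 − 0.5²) / (1 − 0.5^2.5) = 0.750 / 0.823 = 0.911.

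Chance of declaring opioid superiority (noncentral t, 98 df; nominal 1.25%):

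| Window, drug vs placebo | Constant use | Halving every 24 h | Halving every 12 h |
|---|---|---|---|
| 48 vs 60 h | 0.80; 31% | 0.91; 6.5% | 0.97; 2.4% |
| 54 vs 60 h | 0.90; 7.8% | 0.96; 2.8% | 0.99; 1.6% |
| 71 vs 72 h | 0.99; 1.7% | below 1.7% | below 1.7% |

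**3. The reverse direction.** True ratio 0.63, with the drug arm observed for 60 h and placebo for 48 h. The observed ratio becomes 0.63 × 1.25 = 0.787, 0.63 × 1.098 = 0.692 or 0.63 × 1.033 = 0.651. Power falls from 91.5% to 35%, 74% or 87%.

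**4. Opioid noninferiority.** Suppose hourly use on the drug is truly 10% higher, exactly at the margin, and the window cuts the accumulated dose by 10% or 20%. The observed ratio is 1.1 × 0.9 = 0.99 or 1.1 × 0.8 = 0.88. The pass rate rises from 2.5% to about 13% or 42%.

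**5. Effect on pain.** If pain falls linearly from 6 to 3 over 72 h, the TWA to time T is 6 − 3T/144. That is 5.0 at 48 h and 4.75 at 60 h: a shift of 0.25, a quarter of the margin, against the drug.

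**6. The joint claim.** The claim through opioid also needs pain noninferiority. With a 0.25 shift, pain passes with probability 0.459 (SD 2) or 0.697 (SD 1.5). For 48 vs 60 h, in the order of the table columns:
- SD 2: 0.459 × 0.310 = 14%; 0.459 × 0.065 = 3.0%; 0.459 × 0.024 = 1.1%.
- SD 1.5: 22%, 4.5% and 1.6%.
- Equal windows: 0.697 × 0.0125 = 0.9% (SD 2) and 0.910 × 0.0125 = 1.1% (SD 1.5).

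**7. Would dose per observed hour repair it?** The ratio is multiplied by 60/48 = 1.25. Under constant use this is exact: 0.80 becomes 1.00. With declining use it over-corrects: 0.911 becomes 1.14 and 0.968 becomes 1.21, both beyond the 1.1 margin.

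**8. The pain texts side by side.** Section 3.2 has mornings only and stops at discharge. Section 4.5 has the same mornings with no stop. Section 6.4 is four-hourly to 72 h with no stop. They differ in both frequency and end point, so one patient can have three different TWAs.

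**The case against.** - **A wholly inert drug does no harm here.** Randomisation would give both arms the same discharge pattern, and the test would keep its level. This stands. The inflated figures need a drug that shortens stay without changing hourly opioid use. If earlier discharge came from better pain control, a claim of better analgesia would not be entirely wrong.
- **The lead scenario is strong.** Twelve hours' difference with flat use over 60 h is a severe case. If patients leave because their use is already low, less dose is missed. This also stands, so the 31% is an upper illustration. In the milder 54 vs 60 h case, the same method with a 0.125-point pain shift gives joint rates of 4.5%, 1.6% and 0.95% (SD 2).
- **The reverse case runs against the hypothesised mechanism.** True. It shows only that the error has no fixed sign.
- **The calendar labels the treatment phase as inpatient, which suggests stays near 72 h.** This is weak: the same label covers the two days before surgery, and calls for patients discharged early are built in.
- **The pain conflict may be mainly one of frequency.** Section 4.5 says scores are documented in the hospital record, and the discharge limit in Section 7.2 may apply to opioid only. Both readings are possible. That ambiguity is itself a reason to reconcile the texts.
- **Dose per hour could serve.** At 54 vs 60 h it gives 1.07 and 1.096, inside the margin. It still over-corrects whenever use declines.

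**Conclusion.** The concern holds. The hypothesis covers 72 hours; the analysed opioid total covers only the hospital part of them, and the trial expects the drug to change how long that part lasts. This follows from the text alone, as does the conflict between the pain schedules. The size of the bias does not: it depends on unstated discharge times and opioid use over time, and ranges from negligible, if nearly everyone stays 72 h, to severe, with a 12 h difference and flat use. The single-test figures are not the trial's overall error rate; the joint rates are lower and rest on the assumed pain SD and on independence. The point should be fixed, but on these figures it does not by itself invalidate the design.

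**What to change.** - **Window.** Define both primary outcomes over 0–72 h for every patient, whether or not discharged, and use that definition in Sections 2, 3.2 and 7.2.
- **Pain schedule.** Reconcile Sections 3.2, 4.5, 6.4 and 7.2 into one set of assessment times, and state how the TWA is computed from them.
- **Calls.** At the planned daily calls, record the type and dose of opioid taken since the last contact and the current pain score. Convert with the Section 3.2 equivalences, extended to any other opioid reported, and add to the inpatient data.
- **Missing data.** Each call covers all time since the last contact, so a later call recovers a missed one. Gaps that remain, including a missed final call, are multiply imputed using arm, surgery type and last inpatient dose.
- **Sensitivity and reporting.** Keep the in-hospital total as a sensitivity analysis and report hours observed by arm. Do not make dose per observed hour the primary correction.

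The cost is two questions on calls already scheduled, a longer conversion table, a missing-data rule and revised wording. The downside is that home intake is self-reported and noisier than charted doses. The switch from charted to reported data may also fall differently in the two arms, and some calls will be missed.
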